1.1 Synopsis

Protocol Title: An Open-label, Single-arm, Phase II Study of Regorafenib and Nivolumab in Patients with mismatch repair-proficient (pMMR)/Microsatellite Stable (MSS) Colorectal Cancer (CRC)

Short Title: Regorafenib and Nivolumab in pMMR/MSS CRC

CCI

Objectives and Endpoints:

Table 1–1: Objectives and Endpoints

Objectives	Endpoints
Primary	

 To evaluate efficacy of the regorafenib and nivolumab combination^a 	
 ORR per RECIST v1.1^a
Secondary	

 Further evaluation of the efficacy of the regorafenib and nivolumab combination by measuring progression and survival intervals To evaluate safety of the combination 	
 Duration of Response (DOR)^a Disease control rate (DCR) at 8 and 16 weeks^a Progression free survival (PFS)^a Overall survival (OS) Incidence and severity of AEs per CTCAE v5
CCI	
CCI	

CCI AE = adverse event; CTCAE = common terminology criteria for adverse events; iRECIST = response evaluation criteria in solid tumors for trials testing immunotherapeutics; DCR = disease control rate; DOR = duration of response; ORR = objective response rate; OS = overall survival; PFS = progression free survival; CCI RECIST = response evaluation criteria in solid tumors

a) The efficacy endpoints will be based on the local Investigator’s assessment according to RECIST 1.1.

Overall Design:

Disclosure Statement:

This is an open-label, single-arm, Phase II Study of Regorafenib in combination with Nivolumab in participants with pMMR/MSS CRC.

Number of Participants: Recruitment has been stopped at 70 treated patients.

In Amendment 1, it was planned that: approximately 143 participants will be screened to achieve 100 treated participants of which approximately 50-60 participants would have a left sided primary tumor. In order to allow appropriate balance of participants with right and left sided primary tumors, enrollment may be restricted to either left or right sided tumors during the study. (Information about right and left sided primary tumors of the participant will be recorded by the investigator or delegate in the Interactive voice/web response system (IxRS) when the participant is registered in IxRS after signing off the PI/ICF.).

Data Monitoring Committee:

Not applicable.

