9.4.3 Secondary Endpoint(s)

Secondary efficacy endpoints include duration of response (DOR), disease control rate at 8 and 16 weeks, progression free survival (PFS), and overall survival (OS). DOR is defined for responders only as the time from first documentation of response (i.e. CR or PR) until disease progression or death (if death without documented disease progression). Disease control is defined as tumor response of stable disease (SD) or better. PFS is the time from first dose of study medication to disease progression or death, whichever is earlier. For patients who did not progress or die, PFS will be censored at the last evaluable tumor assessment. For patients that started subsequent therapy, PFS will be censored at the start of subsequent therapy. OS is defined as time from first dose to death. For patients who did not die, OS will be censored at the last time point at which the survival status is known to be alive.

For analyses of the secondary endpoints, proportion-based efficacy variables will be using frequency tables as well as 95% two-sided Clopper-Pearson confidence intervals. With regard to time to event data, these will be summarized descriptively using Kaplan Meier methodology and plots, as well as median estimates based on Greenwood's formula, including 95% two-sided confidence interval. Continuous endpoints will be analyzed using summary statistics tables including 95% two-sided confidence intervals.

For the analysis of PFS and OS, PFS and OS rates at specific time points such as 6, 12, and 18 months will also be provided based on the Kaplan-Meier method.

CCI

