The best overall response is the best response recorded from the start of the study intervention until the end of treatment. The participant's best overall response assignment will depend on the findings of both target and non-target disease and will also take into consideration the appearance of new lesions. While some non-target lesions may actually be measurable, they need not be measured and instead should be assessed only qualitatively at the time points specified in the protocol. All participants will have their Best Response on-study classified according to the RECIST v1.1 criteria as outlined below and summarized in [Table 10–3](#).

Complete Response (CR)

Disappearance of all target and non-target lesions. Any pathological lymph nodes (whether target or non-target) must have decreased in size to have a short axis of < 10 mm.

Partial Response (PR)

At least a 30% decrease in the sum of diameters of target lesions taking as reference the baseline sum diameters.

Stable Disease (SD)

Neither sufficient shrinkage to qualify for PR nor sufficient increase to qualify for PD, taking as reference the smallest sum diameters while on study.

Non-CR/Non-PD

To be used for participants with non-target lesions only at baseline. Persistence of one or more non-target lesion(s).

Progressive Disease (PD)

At least a 20% increase in the sum of diameters of target lesions, taking as reference the smallest sum on study (this includes the baseline sum if that is the smallest on study). In addition to the relative increase of 20%, the sum must also demonstrate an absolute increase of at least 5 mm. Unequivocal progression of existing non-target lesions (see comments below), or the appearance of one or more new lesions, also constitutes progressive disease.

Lymph nodes identified as target lesions should always have the actual short axis measurement recorded (measured in the same anatomical plane as the baseline examination), even if the nodes regress to below 10 mm on study. This means that when lymph nodes are included as target lesions, the 'sum' of lesions may not be zero even if complete response criteria are met, since a normal lymph node is defined as having a short axis of < 10 mm.

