To achieve unequivocal progression in participants with measurable disease on the basis of the non-target disease, there must be an overall level of substantial worsening in non-target disease such that, even in presence of SD or PR in target disease, the overall tumor burden has increased sufficiently to merit discontinuation of therapy. A modest 'increase' in the size of one or more non-target lesions is usually not sufficient to qualify for unequivocal.

In the absence of measurable disease, the same general concepts apply here as noted above.

Table 10–2: Target and Non-Target Lesion Response

Target Lesions	Non-Target Lesions	New Lesions	Overall Response	Best Response requires
CR	CR	No	CR	Tumor response is to be documented approximately every 2 cycles (6 weeks) from C1D1. SD requires documentation at least once approximately 2 cycles (6 weeks) from C1D1.
CR	Non-CR/Non-PD	No	PR	
CR	Not evaluated	No	PR	
PR	Non-PD or not all evaluated	No	PR	
SD	Non-PD or not all evaluated	No	SD	
PD	Any	Yes or No	PD	
Any	PD	Yes or No	PD	
Any	Any	Yes	PD	

Abbreviations: C = cycle; CR = complete response; D = day; PD = progressive disease; PR = partial response; SD = stable disease.

Participants with a global deterioration of health current to the objective progression even after discontinuation of treatment without current evidence of disease progression at that time should be reported as “symptomatic deterioration”. Every effort should be made to document the objective progression even after discontinuation of treatment

Table 10–3: Assessment of Best Response According to RECIST v1.1 Criteria for Participants with Non-Target Lesions Only

Non-target lesions	New lesions	Overall response
Complete response	No	Complete response
Non-complete response / Non-progressive disease	No	Non-complete response / non-progressive disease ^a
Not evaluated	No	Not evaluable
Unequivocal progressive disease	Yes or No	Progressive disease
Any	Yes	Progressive disease

a) Non-complete response / non-progressive disease^a is preferred over “stable disease” for non-target lesions.

Response duration

The duration of overall response is measured from the time measurement criteria are first met for CR/PR (whichever is first recorded) until the first date that recurrent or progressive disease is objectively documented (taking as reference for progressive disease the smallest sum of diameters (nadir) recorded on study).

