6.2.3 Secondary endpoints

Overall survival (OS):

Overall survival is defined as the time (days) from the date of first treatment to the date of death.

OS for subjects who are still alive and in the study or who are lost to follow-up at the point of analysis will be censored at the last available date.

OS for subjects who have no post baseline information will be censored at day 1.

Progression free survival (PFS):

PFS is defined as the time (days) from the date of first treatment to the date of radiological or clinical disease progression or death due to any cause, if death occurs before progression is documented.

PFS for subjects without radiological or clinical tumor progression or death at the time of analysis will be censored at their last date of tumor evaluation.

PFS for subjects who have no tumor assessment post baseline and are still alive will be censored at day 1. Patients that report a PD after missed tumor assessment(s) will be censored at the last scan date the patient was known to be progression free.

Disease control rate (DCR):

Disease control rate is defined as the proportion of patients whose best response was complete response (CR), partial response (PR) or stable disease (SD). DCR will be evaluated at 8, 16, 24, 32 and 40 weeks

Scans collected after first progression disease (PD) will not be considered.

Duration of response (DOR):

Duration of response (for PR and CR) is defined as the time (days) from the first documented objective response of PR or CR, whichever is noted earlier, to disease progression or death (if death occurs before progression is documented). Duration of response will be defined for responders only, i.e. subjects with CR or PR.

Time to response (TTR):

Time to response is defined as the time (days) from first treatment until CR or PR and will be derived for responders only.

Duration of stable disease (DoSD):

[figure not shown]

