Duration of stable disease is defined as the time (days) from first treatment to date that disease progression or death (if death occurs before progression) is first documented. This variable will only be calculated for subjects who failed to achieve a best response of CR or PR (i.e. calculated for subjects with SD as best overall response). Also subjects, who have no evaluable tumor assessments post-baseline available, will be excluded. The actual dates that the tumor scans were performed will be used for this calculation. Duration of stable disease for subjects without disease progression or death before progression at the time of analysis will be censored at the date of their last tumor assessment.

For analyses of the secondary endpoints, proportion-based efficacy variables will be using frequency tables as well as 95% two-sided Clopper-Pearson confidence intervals. With regard to time to event data, these will be summarized descriptively using Kaplan-Meier

methodology and plots, as well as median estimates based on Greenwood's formula, including 95% two-sided confidence interval. Kaplan-Meier analysis will be displayed in a table as well, giving the number of patients under risk, the number of events and the number of censoring for time intervals of 3 months duration. Kaplan-Meier Plots will present the number of patients under risk for each time point of the x-axis. Kaplan-Meier Plots and matching tables will be created for the subgroups

- Presence of liver metastases at baseline
- Primary tumor
- Primary side of tumor only.

Continuous endpoints will analyzed using summary statistics tables including 95% two-sided confidence intervals.

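### The SAP defines disease control rate by best response but evaluates it at weeks 8 to 40; applied as written, the rate can never fall after progression or death

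*SAP*

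**What the plan says.** SAP 6.2.3 gives three sentences on disease control rate (DCR). The definition is "Disease control rate is defined as the proportion of patients whose best response was complete response (CR), partial response (PR) or stable disease (SD". The timing is "DCR will be evaluated at 8, 16, 24, 32 and 40 weeks". The only further rule is "Scans collected after first progression disease (PD) will not be considered".

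The protocol lists the secondary endpoint in Table 1-1 as "Disease control rate (DCR) at 8 and 16 weeks", and section 9.4.3 says "Disease control is defined as tumor response of stable disease (SD) or better". The word best does not appear there, and weeks 24, 32 and 40 are not mentioned.

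Protocol 10.7 sets the meaning of best response: "The best overall response is the best response recorded from the start of the study intervention until the end of treatment". Table 10-2 in the same appendix adds that "SD requires documentation at least once approximately 2 cycles (6 weeks) from C1D1". The SAP uses the term in the same cumulative sense for duration of stable disease, which is "calculated for subjects with SD as best overall response".

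Efficacy analyses use the FAS (SAP 6.2), which is the 70 treated patients. Neither document says that progression, death or a missing scan by a given week makes a patient not controlled at that week.

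**The concern.** A rate reported at week 16 is read as the share of patients whose disease is still controlled at week 16. A best-response definition answers a different question: whether control was ever documented. Attaching five time points to it does not turn it into a status measure.

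If the SAP is programmed as worded, the 16-week rate (a protocol-named secondary endpoint), the three later rates and their subgroup tables (SAP 4.8) would not register loss of control. They would also disagree with two outputs in the same report: RECIST results by visit (SAP 6.2.2) and Kaplan-Meier PFS (SAP 6.2.3).

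**Working it through.** The documents state no DCR figure, so there is none to reproduce. The check is first logical, then illustrative.

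**Inputs from the documents**
- FAS denominator: 70, fixed (SAP 5.1, 6.2 and 6.2.1).
- Scans every 8 weeks ±7 days in year 1 (Protocol 8.1), so weeks 8, 16, 24, 32 and 40 are the first five scheduled scans.
- Best response is cumulative, and one qualifying SD scan is enough (Protocol 10.7).
- Scans after first PD are dropped (SAP 6.2.3).

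**Step 1: one patient.** Take SD at week 8 and PD at week 16.
- Best response up to week 16 is SD: controlled.
- Best response over the whole treatment period is SD: controlled.
- Status at the week-16 visit is PD: not controlled.

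Dropping scans after PD removes later scans and leaves the week-8 SD in place. If the patient dies between the two scans there may be no PD scan at all, and the rule has nothing to act on.

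**Step 2: the rate.** Read as best response up to week k, each patient's indicator is a running maximum and can only stay at 0, stay at 1, or go from 0 to 1. The denominator is fixed, so the rate cannot decrease. Read over the whole treatment period, all five rates are identical. Under the up-to-week-k reading the 8-week rate is correct, because only one scheduled scan contributes. From week 16 the rate is at or above the share in control.

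A simulation of 2,000 trials of 70 patients with five visits, allowing PD, death and non-evaluable scans, agrees. The rate fell between time points in 0 trials under either best-response reading and in all 2,000 under status at the visit.

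**Step 3: size per patient.** Each patient with SD or better at week 8 and PD or death by week 16 adds 1/70 = 1.4 percentage points to the week-16 rate.

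**Step 4: illustration (assumed inputs).** Let D be the share controlled at week 8. With a constant progression hazard, status at week 8k is D^k. The written rate is at least D, so the excess is at least D − D^k.

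| D | Status, week 16 (D²) | Excess, week 16 | Excess, week 40 (D − D⁵) |
|---|---|---|---|
| 0.40 | 16.0% | 24.0 points (16.8 patients) | 39.0 points |
| 0.50 | 25.0% | 25.0 points (17.5 patients) | 46.9 points |
| 0.60 | 36.0% | 24.0 points (16.8 patients) | 52.2 points |

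In whole patients for D = 0.50, with 95% Clopper-Pearson intervals at week 16:
- as written, at least 35/70 = 50.0% (37.8 to 62.2);
- by status, 17.5 rounded to 18/70 = 25.7% (16.0 to 37.6).

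**Step 5: freeing the retention rate.** The table forces retention from week 8 to week 16 to equal D. Let retention r vary separately; the week-16 excess is then D(1 − r). For D from 0.40 to 0.60 and r from 0.50 to 0.70 it runs from 0.40 × 0.30 = 12 points to 0.60 × 0.50 = 30 points. With D = 0.50 and r = 0.60, status at week 16 is 21/70 = 30.0% (19.6 to 42.1) against at least 50.0% as written, a gap of 20 points.

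**The case against.** The best defence is that status at each visit was meant all along. Five separate time points make little sense otherwise, since under the only best-response window the documents define, all five rates would be the same number. The contrast with the protocol is also less sharp than it first looks. Protocol 9.4.2, just before the DCR definition, defines response by best overall response, and 9.4.3 does not say how progression, death or missing scans count at weeks 8 and 16. Table 10-2 is imperfect support too, because it equates two cycles with 6 weeks although cycles here last 28 days. Finally, DCR carries no test, and by-visit RECIST results and PFS would show the loss of control anyway.

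Much of this is fair. The intention probably was visit status, and the protocol wording is itself not fully operational. The mismatch in Table 10-2 changes nothing here, since one SD scan at week 8 satisfies the requirement on either count. The statement that the 8-week rate is correct holds only for the up-to-week-k reading; over the whole treatment period, a patient without an evaluable week-8 scan but with SD at week 16 would count at week 8 as well. The 24 to 25 point figure depends on the constant-hazard assumption, and the wider 12 to 30 points shows how much. What remains is that the SAP states a rule, a programmer will follow it, and neither best-response reading gives the share in control at week 16.

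**Conclusion.** The concern holds. As worded, the SAP definition gives a DCR that cannot decline over time and that overstates control from week 16 on whenever a patient controlled at week 8 has since progressed or died. The direction follows from the wording and the fixed denominator and needs no assumption.

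The size is 1.4 points per affected patient, with an unknown total. The illustrative 12 to 30 points at week 16 rests on assumed control of 40 to 60% at week 8 and assumed retention of 50 to 70% to the next scan. Under a constant hazard the week-16 excess cannot exceed 25 points; a rising hazard gives more and a falling hazard less.

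This should be fixed, but it does not threaten the trial's main conclusion. DCR is descriptive, and the ORR test and the sample size do not depend on it.

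**What to change.** In SAP 6.2.3, define DCR at week k as the number of FAS patients with RECIST 1.1 CR, PR or SD at the week-k scan (±7 days, as scheduled in Protocol 8.1) and no PD or death before it, divided by the number in the FAS. If a best-response rate is also wanted, report it once, as an overall figure without a time point.

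State how a missing scan counts. SAP 4.3 says only that missing or unevaluable assessments are neither used nor imputed, which does not settle the matter. One workable choice is to count a missing week-k scan as not controlled, with a sensitivity analysis that counts the patient as controlled if a later scan shows CR, PR or SD with no PD in between. Say explicitly that patients whose scans stopped because of clinical progression or a new anticancer therapy count as not controlled.

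The cost is SAP wording and derivation code. No new data are needed, because a scan is already scheduled at each of the five weeks. Reported rates from week 16 on will be lower, and missed scans add some conservatism of 1.4 points per controlled patient. If 2 to 7 such patients miss the scan (an assumed 3 to 10% of 70), the rate drops by 2/70 = 2.9 to 7/70 = 10.0 points. The sensitivity analysis shows how much of this is due to missed scans.

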6.5 Safety

No formal statistical tests will be done for the safety endpoints. All analyses for safety will be performed in the FAS population.

6.5.1 Extent of exposure

Extent of exposure will be summarized for the FAS, using descriptive statistics.

Duration of study treatment will be calculated in days and presented in months as the date of the last dose of any study treatment – date of the first dose of any study treatment + 1.

Dose modification, if applicable, will be summarized for both treatments separately.

6.5.2 Adverse events

All adverse events (AE) whether considered drug-related or not, will be reported on the CRF with diagnosis, start/stop dates, dates of any grade change, action taken, whether treatment was discontinued, any corrective measures taken, and outcome. For all events, the relationship to treatment and the severity of the event will be determined by the Investigator. AEs will be classified and coded using the National Cancer Institute (NCI) Common Terminology Criteria Adverse Event (CTCAE), version 5.0 .

According to the protocol (See section 8.3.1 of the final study protocol) AE will be collected from the signing of the informed consent form (ICF) until the end of active FU visit, which should be 30 days after last dose of regorafenib and 100 days after last dose of nivolumab. An AE is considered as treatment-emergent (TEAE) if it starts during treatment or within the post-treatment time window.

For further definitions of the terms AE, SAE, seriousness, intensity, causal relationship with treatment, causal relationship to protocol-required procedures, action taken, and outcome please refer to the respective section of the protocol.

In the CRF only the worst action taken with regard to the study medication was captured, if nothing else changed while the AE was ongoing. Therefore all tables using this field, will have a footnote, mentioning this fact.

In addition to standard medDRA grouping, treatment-emergent AE of importance will be defined as follows:

- Rash grade 3 or higher. Rash consists of the following MedDRA LLT*:

10037893, 10037894, 10005876, 10005877, 10012483, 10012884, 10013784, 10013785, 10058692, 10015138, 10015139, 10015143, 10015241, 10015242, 10015243, 10015244, 10015283, 10015285, 10015286, 10015585, 10015587, 10058694, 10058693, 10058721, 10015724, 10015725, 10016064, 10018081, 10018087, 10077181, 10018093, 10018094, 10018095, 10062432, 10062439, 10077163, 10062442, 10062443, 10049201, 10019117, 10024426, 10024437, 10079448, 10062704, 10079449, 10062705, 10025418, 10025422, 10049195, 10025423, 10025424, 10027022, 10027967, 10027968, 10027969, 10027970, 10028837, 10075807, 10074762, 10068748, 10033726, 10033727, 10033728, 10033729, 10033730, 10033737, 10033740, 10034120, 10054770, 10078918, 10074684, 10037844, 10037845, 10037872, 10048332, 10037848, 10037851, 10037855, 10048310, 10037856, 10037858, 10037863, 10037867, 10037868, 10037869, 10037870, 10037873, 10079349, 10037874, 10037875, 10037876, 10037878, 10037880, 10063646, 10066739, 10057984, 10037890, 10059872, 10038183, 10038186, 10038187, 10038188, 10081713, 10082785, 10080343, 10062880, 10040806, 10081571, 10040841, 10040913, 10081143, 10073477, 10047983, 10047984

- High Billirubin (if entered as AE)
- High Liver Enzymes (excluding GGT) (if entered as AE)
 - This table will be broken out by presence of liver metastases (yes vs. no) additionally
- Hand/Foot Syndrom, consisting of the following MedDRA LLT*:
10033552, 10033552, 10070580, 10069640, 10019111, 10048776, 10019126,
10063069, 10033553, 10054524, 10070580, 10069640, 10019111, 10048776,
10019126, 10063069, 10033553, 10054524

All tables for TEAE/TEAE, except the one displaying (S)AE by relationship, will also be broken out by relationship to drug (Rego/Novo/Both). Relationship to drug in this case is defined as:

- Related to Rego: relationship to regorafenib = yes AND relationship to nivolumab = no
- Related to Nivo: relationship to nivolumab = yes AND relationship to regorafenib = no
- Related to Both: relationship to regorafenib = yes AND relationship to nivolumab = yes
- Any related: relationship to regorafenib = yes OR relationship to nivolumab = yes

Descriptive summary tables (frequency and percentage of patients, not of events) will be presented using the most recent version of MedDRA terminology, for the following:

- Overview over treatment-emergent AEs
- Treatment-emergent AEs with grade 3, 4, or 5
- Treatment-emergent AEs by worst CTCAE grade
- Treatment-emergent AEs occurring in at least 5% of patients
- Overview over treatment-emergent AEs leading to study drug withdrawal
- Treatment-emergent AEs leading to study drug withdrawal by worst CTCAE grade
- Treatment-emergent AEs leading to regorafenib dose reduction
- Treatment-emergent AEs leading to drug interruption
- Treatment-emergent AEs leading to dose reduction and/or drug interruption
- Treatment-emergent AEs of importance
- Overview over treatment-emergent drug-related AEs
- Treatment-emergent drug-related AEs with grades 3, 4, or 5
- Treatment-emergent drug-related AEs by worst CTCAE grade
- Treatment-emergent drug-related AEs occurring in at least 5% of patients
- Overview over treatment-emergent drug-related AEs leading to study drug withdrawal

- Treatment-emergent drug-related AEs leading to study drug withdrawal by worst CTCAE grade
- Treatment-emergent drug-related AEs leading to regorafenib dose reduction
- Treatment-emergent drug-related AEs leading to drug interruption
- Treatment-emergent drug-related AEs leading to dose reduction and/or drug interruption

The incidence of pre-treatment AE and non-treatment-emergent AEs during long-term follow-up will be tabulated. Other non-treatment-emergent AE will be presented by means of a subject data listing only.

Overview tables of adverse events will be presented in addition to the frequency tables.

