8.3.1 Time Period and Frequency for Collecting AE and SAE Information

All AEs and SAEs will be collected from the signing of the ICF until the end of active FU visit (30 d after last dose of regorafenib and 100 d after last dose of nivolumab at the time points specified in the SoA (Section [1.3](#))).

Medical occurrences that begin before obtaining informed consent will be recorded on the medical history section of the eCRF. Medical occurrences that begin before the start of study intervention but after obtaining informed consent will be recorded on the AE section of the eCRF. Medical occurrences that started before but deteriorated after obtaining informed consent will be recorded as AEs.

All SAEs will be recorded and reported to the Sponsor or designee immediately and under no circumstance should this exceed 24 hr, as indicated in Section 10.3. The Investigator will submit any updated SAE data to the Sponsor within 24 hr of it being available.

Investigators are not obligated to actively seek AE or SAE after conclusion of the study participation. However, if the Investigator learns of any SAE, including a death, at any time after a participant has been discharged from the study, and he/she considers the event to be reasonably related to the study intervention or study participation, the Investigator must promptly notify the Sponsor.

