9.4.5 Other Safety Analyse(s)

For all safety analyses, the FAS will be used as the FAS definition matches the one of the safety set. The incidence of TEAE (new or worsening from baseline) will be summarized by system organ class and preferred term, severity (based on CTCAE grades), type of AE and relation to study treatment. Deaths reportable as SAEs and non-fatal serious AEs will be listed by participant and tabulated by type of AE. AEs leading to study treatment discontinuation and/or modifications will be summarized. Laboratory abnormalities will be summarized by severity. Frequency and incidence rates will be provided. Frequency tables will also be provided for changes in severity from baseline to worst value post-baseline. Laboratory data considered as AE will be graded according to CTCAE v. 5.0, if applicable. The following summaries will be generated separately for hematology and biochemistry, overall and by cohort with the same dose:

- Frequency table for newly occurring on-treatment all CTCAE grades and CTCAE Grades 3 or 4
- Shift tables using CTCAE grades to compare baseline to the worst on-treatment value

CCI

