10.3.1 Definition of AE

AE Definition

- An AE is any untoward medical occurrence in a patient or clinical study participant, temporally associated with the use of study intervention, whether or not considered related to the study intervention.
- NOTE: An AE can therefore be any unfavorable and unintended sign (including an abnormal laboratory finding), symptom, or disease (new or exacerbated) temporally associated with the use of study intervention.

Events Meeting the AE Definition

- Any abnormal laboratory test results (hematology, clinical chemistry, or urinalysis) or other safety assessments (e.g., ECG, radiological scans, vital signs measurements), including those that worsen from baseline, considered clinically significant in the medical and scientific judgment of the Investigator (i.e., not related to progression of underlying disease).
- Exacerbation of a chronic or intermittent pre-existing condition including either an increase in frequency and/or intensity of the condition.
- New conditions detected or diagnosed after study intervention administration even though it may have been present before the start of the study.
- Signs, symptoms, or the clinical sequelae of a suspected drug-drug interaction.
- Signs, symptoms, or the clinical sequelae of a suspected overdose of either study intervention or a concomitant medication. Overdose per se will not be reported as an AE/SAE unless it is an intentional overdose taken with possible suicidal/self-harming intent. Such overdoses should be reported regardless of sequelae.
- “Lack of efficacy” or “failure of expected pharmacological action” (i.e. disease progression) per se will not be reported as an AE or SAE. Such instances will be captured in the efficacy assessments. However, the signs, symptoms, and/or clinical sequelae resulting from lack of efficacy will be reported as AE or SAE if they fulfil the definition of an AE or SAE.

Events NOT Meeting the AE Definition

- Any clinically significant abnormal laboratory findings or other abnormal safety assessments which are associated with the underlying disease, unless judged by the Investigator to be more severe than expected for the participant’s condition.
- The disease/disorder being studied or expected progression, signs, or symptoms of the disease/disorder being studied, unless more severe than expected for the participant’s condition.

Events NOT Meeting the AE Definition

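### SAP 6.5.2 defines treatment-emergent AEs by start date only, while Protocol 9.4.5 also counts worsening, so on-drug worsening of a screening-onset AE can be left out of the TEAE summaries

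*SAP*

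**What the plan says.** SAP 6.5.2 (Adverse events) gives the rule used for the tables: "An AE is considered as treatment-emergent (TEAE) if it starts during treatment or within the post-treatment time window". It has no criterion for worsening.

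Protocol 9.4.5 describes the same summaries with a wider definition: "The incidence of TEAE (new or worsening from baseline) will be summarized by system organ class and preferred term".

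Four further statements bear on the point:

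- Protocol 8.3.1 puts screening-onset events in the AE data: "Medical occurrences that begin before the start of study intervention but after obtaining informed consent will be recorded on the AE section of the eCRF".
- SAP 6.5.2 lists the CRF items for each AE, including "start/stop dates, dates of any grade change, action taken".
- SAP 6.5.2 refers some terms back to the protocol: "For further definitions of the terms AE, SAE, seriousness, intensity, causal relationship with treatment", followed by procedure-related causality, action taken and outcome. Treatment-emergent is not in that list.
- SAP 6.5.2 gives pre-treatment events their own table: "The incidence of pre-treatment AE and non-treatment-emergent AEs during long-term follow-up will be tabulated".

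**The concern.** The two documents define the same flag differently, and the SAP's version is the narrower one. Screening can last up to 28 days (Protocol 4.1.1). An event that begins in that time at Grade 1 and reaches Grade 3 on study drug is treatment-emergent under the protocol. On a literal reading of the SAP it is not.

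The incidence and severity of AEs is a secondary endpoint. All 19 summaries listed in SAP 6.5.2 and all 9 SAE summaries in SAP 6.5.3 are restricted to treatment-emergent events. They include worst grade, Grade 3 to 5, drug-related events, and events leading to withdrawal, dose reduction or interruption. Any omission works in one direction, towards fewer reported on-treatment events.

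**Working it through.** The plan gives no figure on this point, so the check compares the texts and then works out the scale.

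**1. Applying both definitions to each kind of event**

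| Event | Protocol 9.4.5 | SAP 6.5.2 as written |
|---|---|---|
| Starts on treatment | TEAE | TEAE |
| Starts in the post-treatment window | TEAE (new) | TEAE |
| Present before consent, first worsens on drug | TEAE | TEAE, if the AE is dated from the deterioration |
| Starts in screening, grade does not rise | Not a TEAE | Not a TEAE |
| Starts in screening, grade rises on drug, kept on one record | TEAE | Not a TEAE |
| Starts in screening, grade rises on drug, entered as a new record with its own start date | TEAE | TEAE |

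The definitions part at the fifth row. A condition that predates consent, first deteriorates in screening and worsens again on drug also depends on how the second worsening is recorded.

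**2. Does other text supply the missing criterion?**

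- Protocol 8.3.1 makes an AE of a condition that began before consent and deteriorated after it. It does not address an event that begins between consent and first dose and worsens later.
- The SAP's referral to the protocol does not name TEAE, so the wider definition is not imported that way.
- SAP 4.3 leaves the derivation of treatment-emergent AEs to data management programming, the operations manual and standard guidelines. It states no worsening rule, while SAP 6.5.2 states an explicit rule based on start date.
- The visible part of SAP section 7 does not present the narrower definition as an intended change. The rest is redacted, so nothing can be concluded from it.

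**3. Scale**

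The denominator is the 70 treated patients (SAP 6.2.1). SAP 6.5.2 counts patients, not events.

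- One patient omitted from a rate: 1/70 = 1.43 percentage points.
- Table of events in at least 5% of patients: 0.05 × 70 = 3.5, so 4 patients are needed. 4/70 = 5.71% and 3/70 = 4.29%, so one omission can remove a term from this table.
- Hypothetical example: a true Grade 3 or higher rate of 7/70 = 10.0% would be reported as 6/70 = 8.6% with one omission, or 5/70 = 7.1% with two. This assumes that those patients have no other qualifying event in the same row.

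The documents do not say how many patients have a screening-onset AE that worsens on drug, so the number of omissions cannot be estimated.

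**The case against.** The strongest objection concerns data capture. No text says that a grade change stays on the original record. SAP 6.5.2 says that only the worst action taken was captured where nothing else changed during the event, which hints that another change may open a new entry. Protocol 10.3.1 also counts as an AE an "Exacerbation of a chronic or intermittent pre-existing condition including either an increase in frequency and/or intensity of the condition", so worsening on drug could be read as a new AE that starts on treatment. This stands as a limit on the point: if worsening is entered with its own start date, the SAP rule already captures it. It does not remove the point, because neither text states such a practice or says which date drives the flag.

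A reader might infer more than the documents support:

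- **That these events certainly drop out of every TEAE table.** This depends on the unstated recording practice. Even with one record per event, a patient with another qualifying TEAE stays in the overview and Grade 3 or higher counts.
- **That the events disappear from the report.** They would be in the pre-treatment tabulation and the subject listings (SAP 4.1). SAP 6.5.3 lists non-treatment-emergent SAEs, and its death summaries do not use the flag.
- **That worsening liver enzymes go unseen.** SAP 6.5.5 tabulates laboratory toxicity by worst grade and by change from baseline, whatever the AE start date. Only the tables of bilirubin and liver-enzyme events entered as AEs share the problem.
- **That a sizeable share of patients is affected.** No frequency is given. The event must start before first dose, persist, worsen on drug and not generate a new record. Eligibility also limits unresolved toxicity from prior therapy and abnormal laboratory values.

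It is also fair to say that safety is descriptive, with no formal tests (SAP 6.5), and that SAP 4.3 imputes ambiguous AE dates towards treatment-emergent. That cautious approach sits better with the protocol's definition than with a rule based on onset alone.

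**Conclusion.** The conflict between the definitions is real and should be corrected. Following SAP 6.5.2 literally, on-drug worsening of an AE that began between consent and first dose is left out of the TEAE summaries, although Protocol 9.4.5 counts it. This consequence rests on one assumption that the documents neither confirm nor exclude: that the grade change is kept on the original record.

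The direction of any error is clear, since it can only lower reported on-treatment rates. Its size is not: each affected patient is worth 1.4 points on the rate concerned, and the number of such patients is unknown. No hypothesis test is affected. The correction is worth making because the flag governs nearly all the AE summaries.

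**What to change.** In SAP 6.5.2, define a TEAE as any AE that starts, or worsens in CTCAE grade relative to its pre-treatment grade, on or after first dose and up to 30 days after the last regorafenib dose or 100 days after the last nivolumab dose, whichever is later. That window matches footnote f of the Schedule of Activities, and it spells out the post-treatment window that the SAP sentence mentions without defining.

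State how the flag is derived: from the recorded grade-change dates or, if a change opens a new record, from the start date of that record. Take the worst grade within the window. If the sponsor prefers the narrower definition, the departure from Protocol 9.4.5 should be documented in SAP section 7 with its reason.

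The cost is one sentence and one extra derivation. No new data are needed, because the SAP lists "dates of any grade change" among the CRF items. Reported TEAE rates may rise slightly.
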